### **3.7 Treatment assignment and treatment groups**

This is an open label, single arm study.

Treatment group at the completion of PA0008 (presented as ‘BKZ 160mg’ or ‘BKZ 320mg’) and an overall ‘BKZ Total’ column will be used to summarize data in PA0009.

The endpoints assessing maintenance of ACR and PASI response over time will be summarized by treatment sequence across PA0008 and PA0009. Treatment sequences take the form ‘A/B/C’, where A is the treatment in the first 12 weeks of PA0008, B is the treatment from Week 12 to Week 48 of PA0008, and C is the treatment in PA0009. The seven planned treatment sequences are as follows:

- Placebo/BKZ 160mg/BKZ 160mg.
- Placebo/BKZ 320mg/BKZ 160mg.
- BKZ 16mg/BKZ 160mg/BKZ 160mg.
- BKZ 16mg/BKZ 320mg/BKZ 160mg.
- BKZ 160mg loading dose (LD)/BKZ 160mg/BKZ 160mg.
- BKZ 160mg/BKZ 160mg/BKZ 160mg.
- BKZ 320mg/BKZ 320mg/BKZ 160mg.

For safety summaries the following will be presented:

- Safety summaries including PA0009 data only will be presented by treatment group at the completion of PA0008 and overall.
- Safety summaries including data from both PA0008 and PA0009 combined will be presented for 'BKZ 160mg', 'BKZ 320mg', and 'BKZ Total'. The assignment of each of the sequences to the columns in this table is presented in [Table 3-2](#).
  - The 'BKZ 160mg' treatment column in these tables will include subjects in both the BKZ 160mgLD and BKZ 160mg treatment groups.
  - For each column, only those periods for which the specified treatment is received will contribute to the summary ie, for sequence BKZ 16mg/BKZ 320mg/BKZ 160mg, the 16mg period will contribute to the BKZ Total column only, the BKZ 320mg period will contribute to the BKZ 320mg column and the BKZ Total column only, and the BKZ 160mg period will contribute to the BKZ 160mg column and the BKZ Total column only.

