**Table 10-2: Exposure time at risk**

Exposure Category	Start Date	End Date	Duration of Exposure
Total BKZ exposure	First dose of BKZ in PA0008	Last dose of BKZ in PA0009	Minimum of (End date – start date + 140 a ) and (Date of last clinical contact b – start date + 1)
Total exposure to BKZ 160mgLD and 160mg	First dose of BKZ 160mgLD or 160mg in PA0008 or PA0009	Last dose of BKZ 160mg in PA0009	Minimum of (End date – start date + 140 a ) and (Date of last clinical contact b – start date + 1)
Exposure to BKZ 320mg	First dose of BKZ 320mg in PA0008	First dose of BKZ 160mg in PA0009 for subjects who were dosed in PA0009 c .  Last dose of BKZ 320mg in PA0008 for subjects who were not dosed in PA0009	(End date – start date + 1) for subjects who were dosed in PA0009.  Minimum of (End date – start date + 140 a ) and (Date of last clinical contact b – start date + 1) for subjects who were not dosed in PA0009.
Exposure to BKZ 160mg in PA0009	First dose of BKZ 160mg in PA0009	Last dose of BKZ 160mg in PA0009	Minimum of (End date – start date + 140 a ) and (Date of last clinical contact b – start date + 1)

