Summaries of AEs in PA0008 and PA0009 combined will include AEs with onset on the first dose of bimekizumab in PA0008 up to 140 days after the last dose of bimekizumab in PA0009. AEs which occur on the day of a treatment switch will be considered to have begun on the previous treatment, with the exception of the following AEs which will be considered to have begun on the new treatment:

- Events that fulfill the anaphylaxis criteria for acute events (see [Section 10.2.3](#)).
- Events that fulfill the hypersensitivity reaction criteria for (see [Section 10.2.3](#)).
- Events with a HLT of “Administration site reactions NEC”.
- Events with an HLT of “Injection site reactions”.

AEs that occur on the first day of bimekizumab treatment in PA0008 following initial treatment with placebo will not be included in the summaries, unless they fulfill 1 of the 4 exception criteria above. AEs that occur after the last dose of bimekizumab in PA0009 and up to 140 days after the last dose of bimekizumab in PA0009 will be assigned to bimekizumab 160mg.

AEs will be presented as “number of subjects (percentage of subjects) [number of events]”. “[number of events]” will include all cases of an AE including repeat occurrences in individual subjects, while “number of subjects” will count each subject only once.

An overview of TEAE (number and percentage of subjects with any TEAE, serious TEAE, TEAE leading to study discontinuation, TEAE leading to permanent withdrawal of study medication, drug-related TEAE, severe TEAE, fatal AE [see note below], fatal TEAE and TEAE

with missing seriousness) will be provided by treatment group at completion of PA0008 and overall. This summary will be repeated by SS Sub-population.

This table will be repeated including all TEAEs in PA0008 and PA0009 reported for subjects in the PA0009 SS (with the exception of those with onset during placebo treatment) combined. The 'BKZ 160mg' treatment column in this table will include subjects in both the BKZ 160mgLD and BKZ 160mg treatment groups.

The category for fatal AEs will be based on all subjects enrolled in PA0009 in all the above summaries.

The following categories of TEAE will be summarized by MedDRA SOC, HLT and PT including EAIR and EAER (calculated as described in [Section 10.2.2](#)), where all summaries refer to AEs reported in PA0009 only except where stated:

- All TEAEs by treatment group at completion of PA0008 and overall.

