### 10.2.2 Exposure-adjusted incidence rate and exposure-adjusted event rate

The time at risk (in days) at AE onset is the same as the time since first bimekizumab dose as described in [Section 10.2.1](#).

Total time at risk (as defined in [Section 10.1](#)) and time at risk at AE onset will be divided by 365.25 to give years at risk.

EAIR and EAER will be calculated separately for tables including all events in PA0008 and PA0009 combined, and for tables including events with onset in PA0009 only. The former tables will use time at risk relative to the start date of bimekizumab 160mg/160mgLD or 320mg (for the 'BKZ 160mg' [this includes both BKZ 160mg and BKZ 160mgLD] and 'BKZ 320mg' columns) and time at risk relative to the date of the first dose of bimekizumab (for the 'BKZ Total' column). The latter table will use time at risk relative to the start date of study medication in PA0009.

The EAIR is defined as the number of subjects with a specific AE adjusted for exposure and will be scaled to 100 subject-years:

$$EAIR = 100 * \frac{n_{AE}}{\sum_{i=1}^{n_{AE}} T_{Exp,i} + \sum_{j=1}^{n_{noAE}} T_{Risk,j}} \quad (23)$$

where  $n_{AE}$  is the number of subjects with the AE,  $T_{Exp,i}$  is a subject's time at risk at AE onset in years (equation [16] in years) and  $T_{Risk,j}$  is the total time at risk in years for subjects who did not experience the AE of interest.

If a subject has multiple events at the level of coding evaluated, the time at risk at AE onset is calculated from the first occurrence of the AE.

Exact Poisson 95% CIs for incidence rates are calculated using the relationship between the Poisson and the chi-square distribution (Ulm, 1990; Fay and Feuer, 1997):

$$LCL = \frac{\chi_{2n, \frac{\alpha}{2}}^2}{2} \quad (24)$$

$$UCL = \frac{\chi_{2(n+1), 1-\alpha/2}^2}{2} \quad (25)$$

$$CI_{Lower} = 100 * \frac{LCL}{\sum_{i=1}^{n_{AE}} T_{Exp,i} + \sum_{j=1}^{n_{noAE}} T_{Risk,j}} \quad (26)$$

$$CI_{Upper} = 100 * \frac{UCL}{\sum_{i=1}^{n_{AE}} T_{Exp,i} + \sum_{j=1}^{n_{noAE}} T_{Risk,j}} \quad (27)$$

where  $n_{AE}$  is the number of subjects with the AE and is the basis for the number of the degrees of freedom for the chi-square quantile for the upper tail probability  $\chi^2$ ,  $T_{Exp,i}$  is a subject's time at risk at AE onset in years,  $n_{noAE}$  is the number of subjects without the AE and  $T_{Risk,j}$  the total time at risk for subjects who did not experience the AE.

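### The combined PA0008+PA0009 TEAE overview sets 160mg beside 320mg without exposure-adjusted rates, although planned time at risk is 120–168 weeks on 160mg and 36–48 weeks on 320mg; the severe and drug-related rows have no adjusted counterpart.

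*SAP*

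**What the plan says.** SAP 10.2 specifies the overview as follows: "An overview of TEAE (number and percentage of subjects with any TEAE, serious TEAE, TEAE leading to study discontinuation", continuing with permanent withdrawal of study medication, drug-related, severe and fatal events. A later sentence repeats it for the two studies together: "This table will be repeated including all TEAEs in PA0008 and PA0009 reported for subjects in the PA0009 SS". No exposure-adjusted rate is listed for either version. The general AE display format in the same section would add at most a raw event count.

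SAP 3.7 sets the columns. "Safety summaries including data from both PA0008 and PA0009 combined will be presented for" BKZ 160mg, BKZ 320mg and BKZ Total, and "For each column, only those periods for which the specified treatment is received will contribute to the summary". A subject treated with 320mg in PA0008 therefore appears in both dose columns.

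Table 10-2 ends 320mg time at risk at "First dose of BKZ 160mg in PA0009 for subjects who were dosed in PA0009". Time on 160mg runs to the last PA0009 dose and, subject to last clinical contact, includes a 140-day tail. SAP 10.2 assigns events in that tail to 160mg.

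Exposure adjustment is planned elsewhere for the same data. SAP 10.2.2 says "EAIR and EAER will be calculated separately for tables including all events in PA0008 and PA0009 combined", and SAP 10.2 lists combined SOC/HLT/PT tables with EAIR and EAER for all TEAEs and for serious TEAEs, by dose at onset.

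**The concern.** In the PA0009-only overview the columns are the dose groups carried over from PA0008. Both groups have the same planned follow-up, so percentages are a fair description. In the combined version the columns are doses received, and the design gives 160mg roughly three times the observation time. A percentage of subjects with at least one event rises with time observed, so the two columns would differ even if the doses carried identical risk.

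The overview is the table most readers go to first. A higher percentage of severe or drug-related events on 160mg could be taken as a dose finding, or a real excess on 320mg could be hidden. For these two rows no other combined table by dose would correct the impression.

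**Working it through.** **The plan's own figures.** Treatment to Week 100 plus a 20-week tail gives 100 + 20 = 120 weeks (700 + 140 = 840 days), matching the 120-week maximum in Protocol 5.1.2. Dosing every 4 weeks gives 100/4 + 1 = 26 doses, matching SAP 7.

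**Windows per completer.** SAP 3.7 states that "B is the treatment from Week 12 to Week 48 of PA0008", which is 36 weeks; the first PA0008 period is 12 weeks. One planned sequence, "BKZ 320mg/BKZ 320mg/BKZ 160mg", has 320mg throughout PA0008.

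| Sequence | 160mg column (weeks) | 320mg column (weeks) |
|---|---|---|
| 160mg or 160mg LD throughout PA0008 | 12 + 36 + 120 = 168 | – |
| Placebo or 16mg, then 160mg | 36 + 120 = 156 | – |
| Placebo or 16mg, then 320mg | 120 | 36 |
| 320mg throughout PA0008 | 120 | 12 + 36 = 48 |

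**Assumptions, not in the documents.** Five equal PA0008 arms; placebo and 16mg split 1:1 at Week 12; everyone completes; the same constant hazard on both doses. The 160mg column is then 40% at 168, 20% at 156 and 40% at 120 weeks, with mean 0.4×168 + 0.2×156 + 0.4×120 = 146.4 weeks. The 320mg column is half at 48 and half at 36 weeks, with mean 42.0. The ratio of means is 146.4/42.0 = 3.49.

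**Expected percentages.** For a rate λ per patient-year and w weeks, P = 1 − exp(−λ·w/52.18), averaged over the sequences in a column. At λ = 0.05:
- 160mg: 0.4×14.9% + 0.2×13.9% + 0.4×10.9% = 13.1%
- 320mg: 0.5×4.5% + 0.5×3.4% = 3.9%
- unrounded ratio: 3.31

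| Rate per 100 patient-years | 160mg | 320mg | Ratio |
|---|---|---|---|
| 1 | 2.8% | 0.8% | 3.45 |
| 5 | 13.1% | 3.9% | 3.31 |
| 10 | 24.4% | 7.7% | 3.16 |
| 30 | 56.6% | 21.4% | 2.64 |
| 50 | 74.9% | 33.0% | 2.27 |
| 70 | 85.3% | 42.9% | 1.99 |
| 100 | 93.4% | 55.0% | 1.70 |
| 200 | 99.5% | 79.5% | 1.25 |
| 300 | 100.0% | 90.5% | 1.10 |

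The ratio is 3.4 at about 2.5 per 100 patient-years and 2 at about 69.

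**Sensitivity.**
- *Allocation.* At 5 per 100 the lowest 160mg sequence (120 weeks, 10.9%) still exceeds the highest 320mg sequence (48 weeks, 4.5%), so the direction does not depend on allocation.
- *Same subjects.* Among subjects who received 320mg (120 against a mean of 42 weeks), the ratio is 2.75 at 5 per 100 and 2.07 at 50.
- *Early stopping.* If 10–30% stop uniformly during PA0009, the ratio is 3.21–2.99 at 5 per 100 and 1.95–1.88 at 70.
- *Unequal hazards.* If 320mg truly carried twice the rate (10 against 5 per 100), the table would show 7.7% on 320mg and 13.1% on 160mg, reversing the order.

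**Effect of adjustment.** EAIR (formula 23) divides subjects with an event by time to first event or end of risk. Under a constant hazard a sequence's expected numerator is P and its expected time is P/λ, so each column returns 100·λ: 5.0 on both doses, ratio 1.00.

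**The case against.** Several points on the other side stand.

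- **Existing rate tables.** A reader might infer that the combined safety analysis rests on raw percentages alone. It does not. The primary safety variables are any TEAE and serious TEAE, and both have combined EAIR/EAER tables in the same three columns.
- **Derivable event rates.** Nor is a rate for the remaining rows wholly out of reach. If the overview follows the general AE format, its event counts can be divided by the patient-years in the combined exposure table (SAP 10.1) to give an EAER. The printed rate, and any EAIR, would still be missing.
- **General statements of intent.** SAP 3.10 promises that safety displays using PA0008 data will take PA0008 exposure into account, and SAP 10.2.2 speaks of rates for combined tables. Neither names the overview, whose own definition lists only counts and percentages. They show intent but do not settle the content of this table.
- **No universal factor.** A reader might take 2 to 3.4 as applying to every row. The documents supply neither event rates nor allocation. For a common row such as any TEAE the ratio is 1.8 if 50% on 320mg have an event, 1.4 at 70% and 1.1 at 90%.
- **No planned test.** This is a single-arm, descriptive extension with no dose-comparison objective. The side-by-side columns invite a comparison but do not constitute one.
- **Rates do not rescue every row.** A reader might infer that EAIR would repair the whole table. Protocol 6.1 admits only subjects who completed PA0008 without meeting withdrawal criteria, and the table is limited to the PA0009 Safety Set. Fatal events and events leading to stopping during 320mg treatment are therefore almost absent by selection; the exceptions are events that began on 320mg and had that consequence later. An adjusted rate there would be near zero whatever the true risk.

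**Conclusion.** The point holds in limited form. The combined overview, as specified, shows 160mg and 320mg without exposure adjustment, over planned completer windows of 120–168 and 36–48 weeks. Under equal constant hazards, full completion and equal lead-in arms, events at roughly 2.5 to 69 per 100 patient-years would look about 3.4 to 2 times as frequent on 160mg, with a smaller distortion for commoner events. The direction is robust to allocation and to moderate early stopping; the exact factor is not. What remains uncorrected elsewhere is mainly the severe and drug-related rows. The fatal, study-discontinuation and permanent-withdrawal rows have a separate selection problem that rates do not cure. Because the display is descriptive and the primary variables have rate tables, this should be corrected but does not undermine the primary safety analysis.

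**What to change.** In SAP 10.2, state that the combined overview also gives, for each dose column, patient-years, EAIR with 95% CI and EAER, using the time at risk in Table 10-2. State too that the 160mg and 320mg columns are to be read on these rates and not on the percentages.

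For the fatal, study-discontinuation and permanent-withdrawal rows, add a footnote: only PA0008 completers enter PA0009, so 320mg events in these rows are nearly excluded by design, and neither percentages nor rates should be used to compare doses.

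The cost is a short SAP addition, extra columns and a footnote in one table. The time-at-risk definitions and rate formulas are already specified for the companion tables.

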### 5.1.1 Impact of COVID-19

A listing of all visits affected by COVID-19 will be presented based on the Enrolled Set including the visit, date of visit, relationship to COVID-19, impact category and a narrative (short description) of the event. This data will be summarized by treatment group at completion of PA0008, and overall for the ES for the following:

- Impact of COVID-19 for any reason
- Impact of COVID-19 for any reason by country

In addition, in order to assess the potential impact of COVID-19 on the collection and reporting of efficacy data a separate listing and summary will be presented to display missing data and data collected via an alternative modality (eg, phone, video call). For the purpose of these displays, missing data will be presented only for visits affected by COVID-19 (as reported on the dedicated eCRF page) ie, missing data at other visits and for other reasons will not be included.

The following efficacy assessments may be collected remotely:

- HADS
- HAQ-DI
- SF-36
- PGADA
- PtAAP
- PsAID-9

For visits conducted remotely (as reported on the dedicated eCRF page), it is not possible to assess MASES, PhGADA, BSA, PASI, LDI, TJC or SJC, and therefore these assessments will be missing at the specified visit. In addition, for any missed visit or a visit conducted remotely, the CRP assessment will also be missing. Such assessments will be considered to be missing as a result of COVID-19. For these visits, it will therefore not be possible to assess DAS28(CRP) and may not be possible to classify the subject as an ACR responder or nonresponder.

A listing will be presented showing each impacted visit based on the FAS. This will include the planned visit, the visit date, and details of the assessments conducted remotely and/or those missing as a result of COVID-19.

These data will be presented in a summary table by treatment group at completion of PA0008 and overall for the FAS.

For both the listing and the summary table, only visits at which efficacy assessments are scheduled will be included.

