In addition, the ADAb status will be further classified on a subject level as outlined below:

- **Pre ADAb negative – treatment emergent ADAb negative (Category 1):**
  - Considering PA0009 data only (Category 1a): includes subjects who are ADAb negative at PA0008 Baseline and ADAb negative at all sampling points in PA0009 (including SFU).
  - Considering PA0008 and PA0009 data (Category 1b): includes subjects who are negative at PA0008 Baseline and ADAb negative at all sampling points in PA0008 and PA0009 (including PA0009 SFU).
- **Pre ADAb negative – treatment emergent ADAb positive (Category 2):**

- Considering PA0009 data only (Category 2a): Includes subjects who are negative at PA0008 Baseline and ADA b positive at any sampling point post treatment in PA0009 (up to and including SFU and including the PA0009 EV). This group also includes subjects who have a missing pre-treatment sample (either missing or insufficient volume) at PA0008 Baseline with one or more ADA b positive samples in PA0009.
- Considering PA0008 and PA0009 data (Category 2b): Includes subjects who are negative at PA0008 Baseline and ADA b positive at any sampling point post treatment in PA0008 (up to and including PA0009 SFU). This group also includes subjects who have a missing pre-treatment sample (either missing or insufficient volume) at PA0008 Baseline with one or more ADA b positive samples in PA0008 or PA0009.
- **Pre ADA b positive – treatment emergent reduced ADA b (Category 3):**
  - Considering PA0009 data only (Category 3a): Includes subjects who are positive at PA0008 Baseline, and ADA b negative at all sampling points in PA0009 (including SFU).
  - Considering PA0008 and PA0009 data (Category 3b): Includes subjects who are positive at PA0008 Baseline, and ADA b negative at all sampling points in PA0008 and PA0009 (including SFU).
- **Pre ADA b positive – treatment emergent unaffected ADA b positive (Category 4):**
  - Considering PA0009 data only (Category 4a): Includes subjects who are positive at PA0008 Baseline and are positive at any sampling point in PA0009 (including SFU) with titer values of the same magnitude as PA0008 Baseline (ie, less than a predefined fold increase from the PA0008 Baseline value defined within the validation of the assay).

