  - Considering PA0008 and PA0009 data (Category 4b): Includes subjects who are positive at PA0008 Baseline and are positive at any sampling point in PA0008 or PA0009 (including SFU) with titer values of the same magnitude as PA0008 Baseline (ie, less than a predefined fold increase from the PA0008 Baseline value defined within the validation of the assay).

For the purposes of this study, this is set at an increase of less than or equal to a 3-fold difference from PA0008 Baseline.

- **Pre ADA b positive – treatment emergent ADA b boosted positive (Category 5):**
  - Considering PA0009 data only (Category 5a): Includes subjects who are positive at PA0008 Baseline and are positive at any sampling point post treatment in PA0009 (including PA0009 EV and SFU) with increased titer values compared to PA0008 Baseline.
  - Considering PA0008 and PA0009 data (Category 5b): Includes subjects who are positive at PA0008 Baseline and are positive at any sampling point post treatment in PA0008 or PA0009 (including SFU) with increased titer values compared to PA0008 Baseline.

The increase in titer values is defined as an increase greater than a predefined fold increase from PA0008 Baseline value which is defined within the validation of the assay. For the

purposes of this study, this is set at an increase greater than a 3-fold difference (ie, a minimum of a 4-fold increase).

Note: For any subject who is positive at PA0008 Baseline and positive at a post-Baseline time point, but for whom titers are not available to determine treatment unaffected or treatment boosted status, the subject will be considered as treatment boosted (ie, Category 5), assuming no other samples are available.

- **Inconclusive (Category 6):**
  - Considering PA0009 data only (Category 6a): Includes subjects who have a positive pre-treatment sample at PA0008 Baseline and some PA0009 samples are missing, while other PA0009 samples are ADA b negative.
  - Considering PA0008 and PA0009 data (Category 6b): Includes subjects who have a positive pre-treatment sample at PA0008 Baseline and some PA0008 or PA0009 samples are missing, while other PA0008 and PA0009 samples are all ADA b negative.
- **Total treatment-emergent (Category 7 [Categories 2 and 5 combined]):**
  - Considering PA0009 data only (Category 8a): Includes subjects who are pre ADA b negative – treatment emergent ADA b positive (Category 2a) and pre ADA b positive – treatment boosted ADA b positive (Category 5a).

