  - Considering PA0008 and PA0009 data (Category 8b): Includes subjects who are pre ADA b negative – treatment emergent ADA b positive (Category 2b) and pre ADA b positive – treatment boosted ADA b positive (Category 5b).
- **Total pre ADA b positive (Category 8 [Categories 3, 4, 5 and 6 combined]):** Subjects that are tested ADA b positive at PA0008 Baseline.
- **Missing (Category 9):**
  - Considering PA0009 data only (Category 9a): Includes subjects who have a missing or negative pre-treatment sample at PA0008 Baseline and some PA0009 samples are missing, while other PA0009 samples are ADA b negative.
  - Considering PA0008 and PA0009 data (Category 9b): Includes subjects who have a missing or negative pre-treatment sample at PA0008 Baseline and some PA0008 or PA0009 samples are missing, while other PA0008 and PA0009 samples are all ADA b negative.

The following summaries, figures and listings will be produced:

- Summary tables displaying the number and percentage of subjects with a positive ADA b status at each PA0009 visit and at any visit by treatment group at completion of PA0008. Two tables will be presented:
  - Considering ADA b status in PA0009 only
  - Considering ADA b status in PA0008 and PA0009 (this table will include only the overall summary visits as detailed below).

For the overall summary at any visit 2 summaries will be presented as follows (all summaries exclude data obtained at PA0008 Baseline):

- PA0009 data only: Including any visit during the PA0009 treatment period (as defined in [Section 3.2.2](#)). Thus, this summary will exclude data obtained at the SFU visit and will include data obtained at the PA0009 EV.
- PA0009 data only: Including any visit during PA0009. Thus, this summary will include both data obtained at the SFU visit and at the PA0009 EV.
- PA0008 and PA0009 data: Including any visit during the PA0008 and PA0009 treatment period. Thus, this summary will exclude data obtained at the PA0009 SFU visit.
- PA0008 and PA0009 data: Including any visit during PA0008 and PA0009. Thus, this summary will include data obtained at the PA0009 SFU visit.
- Summary tables (by treatment at completion of PA0008) of the time point of the first occurrence of ADA b treatment-emergent positivity during PA0009, including the PA0009 EV and the SFU visit. This summary will include the following categories:
  - Category 2: Pre ADA b negative – treatment-emergent ADA b positive

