- All TEAEs by treatment group at completion of PA0008 and overall, by SS Sub-population.
- Serious TEAEs by treatment group at completion of PA0008 and overall.
- Serious TEAEs by treatment group at completion of PA0008 and overall, by SS Sub-population.
- All TEAEs in PA0008 and PA0009 by treatment at time of AE onset (BKZ 160mg, BKZ 320mg and BKZ Total).
  - The 'BKZ 160mg' treatment column in this table will include subjects in both the BKZ 160mgLD and BKZ 160mg treatment groups.
- Serious TEAEs in PA0008 and PA0009 by treatment at time of AE onset (BKZ 160mg, BKZ 320mg and BKZ Total).
  - The 'BKZ 160mg' treatment column in this table will include subjects in both the BKZ 160mgLD and BKZ 160mg treatment groups.
- All TEAEs by timing of onset relative to ADAb status in PA0009. This will include columns for the following (regardless of PA0008 Baseline ADAb status):
  - TEAEs starting before the first ADAb positive result in PA0009 including the PA0009 EV (includes ADAb Categories 2a, 4a and 5a).
  - TEAEs starting on the same date or after the first ADAb positive result in PA0009 including the PA0009 EV (includes ADAb Categories 2a, 4a and 5a).
  - TEAEs for subjects who are ADAb negative at all time points in PA0009 including the PA0009 EV (includes ADAb Categories 1a and 3a).

The following categories of TEAE will be summarized by MedDRA SOC, HLT, and PT, by treatment group at completion of PA0008 and overall:

- TEAEs leading to study discontinuation and/or permanent withdrawal of study medication.
- TEAEs leading to permanent withdrawal of study medication.
- TEAEs with a fatal outcome.

- All TEAEs by maximum relationship.
- Serious TEAEs by maximum relationship.
- TEAEs with a fatal outcome by maximum relationship.
- All TEAEs by maximum intensity.
- Non-serious TEAEs reported by more than the reporting threshold of 5% of subjects. The cut-off will be applied before rounding on each treatment group and overall.

A further summary will be presented by treatment group at completion of PA0008 and overall displaying the frequency of TEAEs by descending frequency of PT.

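### The TEAE-by-ADAb table has no column for never-positive subjects with a missing ADAb sample, so its negative comparator is selected on complete sampling

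*SAP*

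**What the plan says.** SAP 10.2 introduces the table of TEAEs by onset relative to ADAb status with the words "This will include columns for the following (regardless of PA0008 Baseline ADA" status). Three columns follow:

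- The first is "TEAEs starting before the first ADA b positive result in PA0009 including the PA0009 EV (includes ADA b Categories 2a, 4a and 5a").
- The second takes events on or after the first positive result, for the same three categories.
- The third takes subjects who are "negative at all time points in PA0009 including the PA0009 EV (includes ADA b Categories 1a and 3a").

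No missing, other or total column is specified. The table belongs to the group reported with EAIR and EAER.

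SAP 9.2 defines the categories. Categories 1a and 3a both require a subject to be "negative at all sampling points in PA0009 (including SFU"). Subjects with a gap are placed elsewhere according to their baseline status. Category 9a is for those whose baseline was not positive: "Includes subjects who have a missing or negative pre-treatment sample at PA0008 Baseline and some PA0009 samples are missing, while other PA0009 samples are", the remainder all testing negative. Category 6a has the same form for subjects positive at baseline: "Includes subjects who have a positive pre-treatment sample at PA0008 Baseline and some PA0009 samples are missing", the others being negative.

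SAP 2.2.5 schedules 9 ADAb samples per subject: EV, Weeks 12, 24, 36, 48, 72, 96 and 104, and SFU.

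**The concern.** The two sides of the comparison have different entry rules. One positive PA0009 sample puts a subject in the before/after columns, however many other samples are missing. A subject who was never positive needs a complete series, SFU included, to be counted as negative. One missing sample removes that subject, and all of that subject's TEAEs, from the table.

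The table exists to show whether adverse events track antibody status. Column membership fixes both the event counts and the person-time behind EAIR and EAER (SAP 10.2.2). If subjects with gaps have different adverse event rates from subjects without them, the contrast between columns reflects sampling completeness as well as antibody status. A reader who adds the columns will also not reach the Safety Set total and will find no explanation in the table.

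**Working it through.** **Step 1: map every subject type to a column.** Cross baseline status (negative, positive, missing) with any PA0009 positive (yes, no) and any PA0009 sample missing (yes, no): 3 × 2 × 2 = 12 combinations. The category definitions are from SAP 9.2 and the column lists from SAP 10.2.

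| PA0008 Baseline | Any PA0009 positive | Any PA0009 sample missing | Category | Column |
|---|---|---|---|---|
| Negative or missing | Yes | Yes or no | 2a | Before/after |
| Positive | Yes | Yes or no | 4a or 5a | Before/after |
| Negative | No | No | 1a | Negative |
| Positive | No | No | 3a | Negative |
| Negative | No | Yes | 9a | None |
| Positive | No | Yes | 6a | None |
| Missing | No | Yes | 9a | None |
| Missing | No | No | None defined | Fits the column's wording, not its category list |

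All 6 combinations with a positive have a column. All 3 never-positive combinations with a gap have none. Reading the third column as covering whatever samples are available does not work, because 6a and 9a exist to take all-negative subjects with gaps out of 1a and 3a.

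**Step 2: illustrate the size.** The plan gives no missing rate and no figure to reproduce. Assume that each of the 9 samples is missing independently with probability p.

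- Left out as written (at least 1 missing): 1 − (1 − p)^9.
- Left out if one missing sample is tolerated (at least 2 missing): 1 − (1 − p)^9 − 9p(1 − p)^8.

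| Assumed p | At least 1 missing | At least 2 missing |
|---|---|---|
| 0.5% | 4.4% | 0.1% |
| 1% | 8.6% | 0.3% |
| 2% | 16.6% | 1.3% |
| 5% | 37.0% | 7.1% |
| 10% | 61.3% | 22.5% |

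Independence is unfavourable here, since gaps from dropout cluster within subjects. If affected subjects miss 4 of 9 samples on average (also an assumption), the share affected is 9p/4: 4.5% at p = 2%, about 11% at 5% and 22.5% at 10%. If only the 4 samples after Week 48 are at risk, 1 − (1 − p)^4 gives 7.8%, 18.5% and 34.4%.

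**Step 3: direction of any bias.** Let the retained never-positive subjects have N1 events over time T1, and those left out N2 events over T2. The EAER without the second group is below the EAER with it only if N2/T2 > N1/T1. Leaving subjects out removes person-time as well as events, and nothing in the documents fixes these rates.

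**Step 4: compare with the plan's own alternative.** In the figure of ACR50 response over time by ADAb group (SAP 9.2), a subject with one missing or inconclusive sample and the rest negative counts as ADAb negative, and a Missing group takes the remainder. The same subject is therefore negative in that figure and absent from the TEAE table.

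**The case against.** Several points on the other side stand.

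- **Early stoppers are sampled.** Withdrawn subjects are asked to attend the ET and SFU visits (Protocol 6.3, 8.10), and both collect ADAb (Protocol 8.8, 8.9). SAP 3.5 maps ET samples to scheduled ADAb visits. This narrows the gap without closing it, because an ET sample fills one scheduled visit only. Someone stopping between Weeks 24 and 36 still has none for Weeks 48, 72, 96 and 104.
- **Missing is not defined for ADAb.** The SAP does not say whether visits after termination count as missing samples. If they do not, negative early stoppers stay in 1a or 3a and the link with adverse events weakens. The wording that requires every PA0009 sampling point, SFU included, points the other way, but this is a reading of the text.
- **Pandemic losses are limited.** SAP 8.5 places the onset after all subjects had completed Week 48, so 5 of the 9 samples were safe. SAP 5.1.1 says that "for any missed visit or a visit conducted remotely, the CRP assessment will also be missing"; it does not mention ADAb, and extending it to another blood draw is inference.
- **The omission is visible and local.** SAP 9.2 plans counts of subjects in each ADAb category, so the size of 6 and 9 will be reported. Every event remains in the main TEAE tables and listings. The wording does not forbid a further column, although none is specified.
- **Caution is defensible.** Declining to call an incompletely sampled subject negative is a reasonable choice. It justifies keeping such subjects out of the negative column, but not out of the table.

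**Conclusion.** The gap in column assignment is certain from the text. Never-positive subjects with at least one missing PA0009 sample, and their TEAEs, have no column, while positive subjects with the same gaps are kept. Subjects with a missing Baseline and a complete negative PA0009 series have no category. The negative comparator is selected on complete sampling, and the columns need not add up to all Safety Set TEAEs.

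A reader might infer that incidence, EAIR and EAER in the negative column are biased low, so that the table leans towards showing harm from antibodies. The documents do not support that. Step 3 shows that the sign depends on unknown rates, and crude incidence could even rise, since the retained subjects have the longest follow-up. Gaps arising purely at random would shrink the column without biasing it. The supportable statement is that the contrast could be biased in a direction and by an amount that cannot be determined from the plan.

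The 17% at p = 2% depends on an assumed rate and on independence; clustering lowers it. This is one descriptive table in a single-arm study, and the primary safety analyses are untouched. It is worth correcting because the defect is specific and the remedy nearly free.

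**What to change.** In SAP 10.2:

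1. Add a fourth column for never-positive subjects with incomplete PA0009 sampling (Categories 6a and 9a), so that every Safety Set TEAE appears. Wording it by that description would also catch a subject with no evaluable PA0009 sample, whom neither category covers because each requires some negative results.
2. Assign subjects with a missing PA0008 Baseline and all-negative, complete PA0009 samples to the negative column, and give them a category in SAP 9.2.
3. State whether visits after early termination count as missing samples.
4. Optionally, count a subject with only one missing sample and the rest negative as ADAb negative, as in the ACR50-by-ADAb figure, and keep the complete-sample version as a sensitivity table. Borrow only the tolerance for a missing sample: that figure also requires two positive samples before it calls a subject positive, which this table does not.

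A looser rule, calling a subject negative on a single post-EV sample, is not recommended, because it could label about two years of follow-up negative on one result.

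The cost is one extra column and a few lines of SAP text, with no new data. If the tolerance in item 4 is used, a few subjects with undetected positivity at the missed sample may be counted as negative.
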